### **Procedures**

\* BodiTrak. Model BT1526-8578. Vista Medical Ltd [name]

† iPad. Apple Inc. [name]

‡ Body Align Pro. serial number 86300861. Motion Unlimited Corporation California. [name].

During Phase I, individuals in both groups sat unsupported on a hi-lo mat table which was adjusted so participants were sitting at 90 degrees hip and knee flexion with feet shoulder width apart. Tape marks were used to mark initial set up ensuring standardized positioning for each trial. Following baseline trials, all participants watched the same instructional video describing lateral weight shifting. The instructions included correct mechanics that should be used when weight shifting laterally with focus on correct form needed for the movement.

Testing included baseline, acquisition, short term retention (5 minutes later), and long-term retention (7-10 days later). Participants performed three trials of seated weight shifting to each side at all timepoints. During acquisition, the internal focus group was instructed to “shift your weight as much as possible towards your right or left hip without using your arms”. The external focus group sat with targets one arm length away at shoulder height and were instructed to “shift your body weight as much as possible towards the blue/orange target without using your arms.” During baseline and retention trials, adults were instructed to “lean as far as you can to the right/left without using your arms.” During Phase II, the protocol was similar except 6 trials were performed for acquisition to potentially improve motor learning, which was not significant in Phase I per retention data. Other changes to the protocol included allowing participants to move their feet when weight-shifting. Instructions were also revised. The external focus group was told to “move your shoulder as close to the blue/orange target as possible”, while the internal focus group was told to “shift your body weight as much as possible towards your right/left hip without using your arms.” These instructions were too dissimilar and had

\* BodiTrak. Model BT1526-8578. Vista Medical Ltd [name]

† iPad. Apple Inc. [name]

‡ Body Align Pro. serial number 86300861. Motion Unlimited Corporation California. [name].

participants thinking about different body areas, shoulder as opposed to hip. The external focus instructions were also mixed since the shoulder was mentioned.

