### **Outcome measures**

A 32X32 array BodiTrak\* pressure mat with an 18.125 in x 18.125 in sensing area (1,024 sensors) was used to measure lateral excursion of center of pressure during each trial for both phases. The pressure mat has a 200 mmHg calibration range and up to 150 Hz sampling frame rate. During Phase II, a 9.5" X 7.31" X 0.37" 4th generation iPad†, with a 9.7-inch retina display, was used to record videos of each trial. The iPad has a 1080p HD video and 1.2 MP photo camera with autofocus and a 2.4 aperture with video stabilization. From this footage, shoulder alignment was measured during seated lateral weight shifting using the Body Align Pro app‡, trademarked on Nov. 28, 2014. Markers were placed at the acromion bilaterally. Each trial was recorded, and snap shots of the furthest lateral weight shift were uploaded into the software. The software then allowed angles to be drawn using a line from acromion to acromion compared to a horizontal plumb line (see Figure 1). This measurement was used to evaluate the participants ability to move their trunk in accordance with the instructions given, keeping their shoulders parallel to the horizontal. Validity and reliability tests are currently being conducted for this measurement method.

Insert Figure 1.

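### Do the unmatched Phase II instruction scripts call for a change to how the Phase II group contrast is analysed or described?

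*Combined protocol and SAP*

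**What the plan says.** Procedures prints five scripts. In Phase I acquisition, the internal group was asked to shift weight toward the hip, and the external group to "shift your body weight as much as possible towards the blue/orange target without using your arms"; both scripts forbid use of the arms. Baseline and retention used one script for both groups: "lean as far as you can to the right/left without using your arms".

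For Phase II, "the protocol was similar except 6 trials were performed for acquisition to potentially improve motor learning". The section adds that participants could now move their feet and that the instructions were revised. The external script became "move your shoulder as close to the blue/orange target as possible" and the internal script "shift your body weight as much as possible towards your right/left hip without using your arms".

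The same section then criticises this revision. It says "These instructions were too dissimilar and had" participants attending to different parts of the body, the shoulder in one group and the hip in the other. It adds: "The external focus instructions were also mixed since the shoulder was mentioned".

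Data analyses says the Phase I ANOVA examined whether the demonstration, instructions and set-up separated the two focus groups. It describes the Phase II ANOVAs (group by three and group by four timepoints) as relating focus of attention to performance. It does not mention the script limitation.

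**The concern.** A comparison of internal with external focus is clean only if the scripts differ in focus and in nothing else. The Phase I pair came close: both asked for a weight shift and both carried the arms clause. The Phase II pair does not. The external script asks for a different action, names a body part and, as printed, leaves out the arms clause. The stated limitation names the body-part difference and the mixed cue but not the arms clause.

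If the external group was free to use its arms at acquisition and the internal group was not, lateral centre-of-pressure excursion could differ between groups for a reason unrelated to attention. Someone who read only Data analyses would then take a Phase II group-by-time effect as a focus effect. The study is also meant to prepare for a later randomized trial, so a fault left unnamed might be carried forward.

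**Working it through.** The documents give no figure to reproduce on this point. The check is a comparison of the printed scripts, followed by where a script effect would enter the model.

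**Step 1: the scripts side by side (Procedures).**

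| Script | Action | Reference point | Arms clause |
|---|---|---|---|
| Phase I internal | shift weight | hip | yes |
| Phase I external | shift body weight | coloured target | yes |
| Baseline and retention, both groups | lean | right or left | yes |
| Phase II internal | shift body weight | hip | yes |
| Phase II external | move shoulder | coloured target | not printed |

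Four of five carry the clause. Reading the two Phase II scripts as acquisition scripts is an inference from the Phase I structure. That the common script stayed in use in Phase II rests on Phase II being called similar and on no change to that script being printed.

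**Step 2: what is already conceded.** The admission opens in general terms (too dissimilar) and then names two specifics: shoulder against hip, and the mixed external cue. The change of action largely restates the first of these, since moving the shoulder and shifting weight to the hip is the shoulder-hip contrast. Only the arms clause is clearly unnamed.

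**Step 3: where a script effect would enter.** Let b be a shift in the external-minus-internal difference at acquisition that is due to script alone, with no carry-over to other timepoints.

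- Average group difference, three timepoints: (0 + b + 0)/3 = b/3.
- Average group difference, four timepoints: (0 + b + 0 + 0)/4 = b/4.
- Group difference in change from baseline to acquisition: b − 0 = b.

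So the acquisition contrast would carry the whole of b. The documents give neither b nor the variance and correlation of the outcome, so no error rate can be attached.

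Counting post hoc pairs does not help. Acquisition is in 2 of the 3 pairs in the three-timepoint model and 3 of the 6 in the four-timepoint model, but those comparisons are within group. The script changes between the common instruction and acquisition in both groups, and in Phase I as well. The counts therefore do not measure the Phase II mismatch between groups.

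**Step 4: could the analysis separate script from focus?** No. Every external participant was assigned the external script and every internal participant the internal one. Group and script are the same variable, and no covariate or alternative model can split them.

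**Step 5: could the recordings settle it?** Outcome measures says that in Phase II an iPad "was used to record videos of each trial". Acquisition would give at most 26 × 6 × 2 = 312 recordings if six trials were done to each side, or 26 × 6 = 156 if six covers both sides. If these were kept, arm use could be counted by group. The shoulder-hip difference and the mixed cue would remain whatever the count showed, so the contrast would still not isolate focus.

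**Step 6: is there a claim to correct?** Setting reports the Phase I finding of no significant group difference. No Phase II group result or focus conclusion is printed, and no later sample size is built on one.

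**The case for a change.** The strongest argument for a change is that a feasibility study exists to list its own faults fully. A later designer who repairs only the two named faults could leave the arms clause unmatched. Nor can one assume that the clause was spoken: Procedures says the instructions were revised and prints the revision without it, and Investigators reports that inconsistencies in instruction persisted. Phase II also measured shoulder alignment from acromion markers, and only the external script names the shoulder. On this view, two or three sentences would cost almost nothing.

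Part of this stands. The clause is missing as printed, the limitation does not name it, and Data analyses does not point back. A careful author might well add both.

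The rest is weaker. The omission is established only on paper. Procedures calls Phase II similar apart from listed changes, and lifting the arms restriction is not listed; no section reports arm use. A later designer has all five scripts in one section, including the matched Phase I pair, with the statement that the Phase II pair was too dissimilar. The wording in Data analyses gives the purpose of the ANOVA and does not assert an effect, and the Phase I sentence uses the same label for its groups. Investigators already says that training must change before a randomized trial.

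**Conclusion.** The observation is accurate but calls for no change. The Phase II contrast compares two instruction packages, chiefly at acquisition and at retention only through different practice. The authors have said as much in general terms. The scripts have already been delivered, group and script cannot be separated by analysis, and no printed conclusion depends on treating the difference as focus alone. Naming the arms clause or adding a cross-reference would tidy the text without altering any model, estimate or result.

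The residue is one clause missing from one of five printed scripts and one absent cross-reference. Its effect on the outcome is unknown. This conclusion rests on three readings: that the Phase II group scripts were used at acquisition, that baseline and retention kept the common script, and that the documents draw no Phase II focus conclusion. A focus-only claim made elsewhere from the Phase II contrast would have to be judged against the limitation already stated in Procedures.

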### **Outcome measures**

A 32X32 array BodiTrak\* pressure mat with an 18.125 in x 18.125 in sensing area (1,024 sensors) was used to measure lateral excursion of center of pressure during each trial for both phases. The pressure mat has a 200 mmHg calibration range and up to 150 Hz sampling frame rate. During Phase II, a 9.5" X 7.31" X 0.37" 4th generation iPad†, with a 9.7-inch retina display, was used to record videos of each trial. The iPad has a 1080p HD video and 1.2 MP photo camera with autofocus and a 2.4 aperture with video stabilization. From this footage, shoulder alignment was measured during seated lateral weight shifting using the Body Align Pro app‡, trademarked on Nov. 28, 2014. Markers were placed at the acromion bilaterally. Each trial was recorded, and snap shots of the furthest lateral weight shift were uploaded into the software. The software then allowed angles to be drawn using a line from acromion to acromion compared to a horizontal plumb line (see Figure 1). This measurement was used to evaluate the participants ability to move their trunk in accordance with the instructions given, keeping their shoulders parallel to the horizontal. Validity and reliability tests are currently being conducted for this measurement method.

Insert Figure 1.

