## **Investigators**

Although the principal investigators were both faculty members at Western Carolina University, one of which was a licensed physical therapist, the other investigators were student physical therapists. During Phase I, each investigator filled one of three roles during data collection for the entire phase: script reading, computer management, or patient guarding. Lack of cross-training created difficulty in data collection, therefore in Phase II investigators were trained for all roles. Different student groups conducted each phase of the feasibility study and were trained primarily by the previous student group. Inconsistencies with both instruction and data collection persisted suggesting changes in investigator training are necessary prior to a randomized controlled study.

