### **Randomization and blinding**

During Phase I, stratified randomization was used based on gender. Results from a 2013 study showed significant differences between gender during focus of attention trials suggesting the potential need for randomization based on gender. Group allocation was randomly selected for the first male and first female participants. Each following participant was alternately placed in either the internal or external focus of attention group. During Phase II, gender-based stratification was not used, to explore whether the intervention groups would naturally be comparable based on gender, age, BMI, and Function in Sitting Test scores. Instead, a blocked randomization with a random number generator (blocks of 10) was used to determine the order of focus group allocation. A blinded statistician and a graduate assistant performed the random number generation and placed the group assignments into separate envelopes, which were then sealed. Group assignment remained in sealed envelopes until after baseline measurements were completed. The participants and statistician were blinded for both phases of the feasibility study.

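### The Phase II shoulder angle depends on a reader's choice of video frame, and no masking of that reader is stated, so any group comparison of this measure is open to detection bias

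*Combined protocol and SAP*

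**What the plan says.** All references are to the combined protocol and SAP.

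- **Outcome measures.** In Phase II an iPad "was used to record videos of each trial". Markers were placed on both acromia. From these recordings, "snap shots of the furthest lateral weight shift were uploaded into the software". The section gives no rule for identifying the furthest shift, names no reader and mentions no duplicate reading. The angle itself was produced by hand in the app: "The software then allowed angles to be drawn using a line from acromion to acromion compared to a horizontal plumb line". On the standing of the method, the section adds: "Validity and reliability tests are currently being conducted for this measurement method". The other outcome, lateral centre-of-pressure excursion, comes from a pressure mat and was used in both phases.
- **Randomization and blinding.** "The participants and statistician were blinded for both phases of the feasibility study". Nobody else is listed. "Group assignment remained in sealed envelopes until after baseline measurements were completed", so allocation was open from acquisition onward.
- **Investigators.** The roles named are reading the script, managing the computer and guarding the patient, and "in Phase II investigators were trained for all roles".
- **Procedures.** Acquisition instructions differ by group, and targets are described for the external focus group. Baseline and retention trials use one neutral instruction for everyone.
- **Data analyses.** Phase II performance is analysed by 2 × 3 and 2 × 4 (group by time) mixed ANOVA. The dependent variable is not named.

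**The concern.** The angle recorded for a trial depends on which frame is taken as the furthest shift. Without a written rule, two readers may stop the same video at different frames and obtain different angles. If the reader knows the group, that choice can drift with expectation. The risk is real here because the angle is meant to show whether the participant moved as instructed, and at acquisition the two groups were instructed differently. A reader who knows the group may expect a particular shoulder posture.

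A small, consistent tendency of this kind would appear in the results as a group difference. The sphericity and Bonferroni corrections planned under Data analyses cannot remove it: they address the degrees of freedom and the number of comparisons, not a shift in the measurements. With reliability testing unfinished, the document also gives no reader-error figure from which to bound the problem.

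**Working it through.** **1. Where judgement enters.** The frame is chosen by a person (implied by the description of snapshots, not stated outright) with no stated rule. The line is also drawn by a person, but it joins two physical markers and is compared with a horizontal reference. Frame choice is the weaker step.

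**2. When a reader could know the group.**

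| Timepoint | Allocation open during the session? | Group-specific cue in the trial? |
|---|---|---|
| Baseline | No | None described |
| Acquisition | Yes | Different script; targets for the external focus group |
| Short- and long-term retention | Yes | None described; same neutral instruction |

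Exposure is greatest at acquisition. At the other timepoints the footage itself gives little away, but a reader who already knew the allocation could still apply that knowledge when the videos were read later.

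**3. Size, as an illustration.** The document gives no figure to reproduce: no SD for the angle, no bias estimate, and no power-analysis numbers. Inputs:

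- 26 participants recruited in Phase II (Recruitment and retention)
- Assumed: equal split, so n = 26 / 2 = 13 per group, with no losses
- Assumed: two-sided 5% test and no true group effect
- Assumed: systematic reading difference between groups of b SD, from 0.1 to 0.5

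The two-sample t-test has 2 × 13 − 2 = 24 degrees of freedom and critical value 2.064. The noncentrality is λ = b × √(n/2) = b × √6.5 = 2.550b. The false-positive rate is P(|T| > 2.064), where T is noncentral t with 24 degrees of freedom and noncentrality λ.

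| b (SD) | λ | False-positive rate |
|---|---|---|
| 0 | 0 | 5.0% |
| 0.1 | 0.255 | 5.7% |
| 0.2 | 0.510 | 7.8% |
| 0.3 | 0.765 | 11.4% |
| 0.4 | 1.020 | 16.5% |
| 0.5 | 1.275 | 23.2% |

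**4. Where it would show in the mixed ANOVA.** Let the reading bias between groups be b.

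- Same bias at every timepoint: the group main effect shifts by b. The group difference in change from baseline to acquisition shifts by b − b = 0, so the group-by-time interaction is untouched.
- Bias at acquisition only: that change contrast shifts by b − 0 = b, so the interaction is affected. The main effect, averaged over timepoints, shifts by b/3 in the 2 × 3 model and b/4 in the 2 × 4 model.

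**5. Workload of a masked re-reading.** Procedures gives three trials per side, that is 6 per timepoint, and 6 trials for Phase II acquisition without saying whether that is in total or per side.

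- Lower count (6 acquisition trials in total, no long-term retention): 26 × (6 + 6 + 6) = 26 × 18 = 468 clips
- Upper count (6 acquisition trials per side, full long-term retention): 26 × (6 + 12 + 6 + 6) = 26 × 30 = 780 clips

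**The case against.** The strongest reply is that the lack of masking is read from silence. The document never says that the reader knew the group, nor who the reader was. That stands: the point is that the measure is open to bias, not that bias occurred.

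A reader might go further and infer from the cross-training that the investigators who delivered the group script also measured the angles. The text does not support this. The roles in which they were trained are the three listed under Investigators, and video reading is not among them. Nothing shows that a session investigator read the videos, and nothing rules it out.

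It might also be inferred that the recordings give the group away throughout. That is too broad. Group-specific instructions occur only at acquisition. The target set-up is described for Phase I and carries into Phase II only through the statement that the protocol was similar and the wording of the instruction. Whether targets fall within the camera's view is not stated, and a still carries no sound.

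Three further replies stand in part. The acromion markers limit the freedom in drawing the line, though not in choosing the frame. Data analyses does not name the shoulder angle as an ANOVA outcome, so its group comparison is inferred from its listing under Outcome measures; if it served only as a check on adherence to instructions, less hangs on it. Finally, this is a feasibility study that already reports inconsistent data collection and unfinished validation. Those admissions counsel caution about the measure, but neither addresses masking.

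**Conclusion.** The concern holds for the Phase II shoulder angle only. Frame choice, and less so line drawing, is a judgement made without a stated rule, and the stated blinding does not extend to whoever made it. A group comparison of this angle cannot be assumed free of detection bias, above all at acquisition. The centre-of-pressure outcome is instrumented and largely unexposed, so the point does not carry over to it.

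The size is unknown. The range of about 6% to 23% false positives, against a nominal 5%, rests on an assumed bias of 0.1 to 0.5 SD, an assumed 13 per group without losses, and a t-test standing in for the mixed ANOVA. At the low end the effect is slight. The table should not be read as an estimate of the actual error rate, because nothing in the document supports a particular bias. Which ANOVA term would be affected depends on whether the bias is constant over time. Even so, the remedy is inexpensive enough that it should be adopted.

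**What to change.** State under Randomization and blinding or Outcome measures who read the videos and whether they were masked to group and timepoint. If they were, that closes the point.

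If they were not, then for a re-reading of these videos (if kept) and for the later randomized study:

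1. Fix the frame by an objective rule. One option is the time of peak centre-of-pressure excursion on the mat, if the two recordings can be aligned. Otherwise apply a written rule to muted video.
2. Give the stills random codes and shuffle them across group and timepoint.
3. Obscure targets where this does not hide an acromion marker. Participants in the external focus group move the shoulder toward the target, so simple cropping may remove the landmark.
4. Have an existing student investigator who did not run that participant's session draw the angles.
5. Release group codes only after all angles are recorded.

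No additional assessor is needed. The cost is file handling for roughly 468 to 780 clips, which batch muting and renaming would reduce, and a rota limit on who may read which participant. Where a target cannot be hidden without losing a marker, masking at acquisition stays incomplete and should be reported as such.
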